5.10.3.3. Hepatobiliary Events

The percentages of patients with treatment-emergent hepatic AEs will be summarized by treatment group using MedDRA PT nested within each SMQ ordered by decreasing frequency. The following SMQs based on MedDRA will be used to identify hepatic events:

- Broad and narrow terms in the Liver related investigations, signs and symptoms SMQ (20000008)
- Broad and narrow terms in the Cholestasis and jaundice of hepatic origin SMQ (20000009)
- Broad and narrow terms in the Hepatitis non-infections SMQ (20000010)
- Broad and narrow terms in the Hepatic failure, fibrosis and cirrhosis and other liver damage SMQ (20000013)

- Narrow terms in the Liver-related coagulation and bleeding disturbances SMQ (20000015)

5.10.3.4. Injection Site Reactions

Injection site reactions will be evaluated using the spontaneous AE reporting of injection site reactions by the selected MedDRA PTs for the LY3209590 study program.

Table BDCL.2 contains a list of MedDRA PTs based on MedDRA (both narrow and broad scope) that will be used to identify potential injection site reaction from the spontaneous reported AEs.

The number and percentage of patients experiencing treatment-emergent potential injection site reaction identified using broad and narrow search strategy will be summarized and compared by treatment group using Fisher's exact test. The number and percentage of patients experiencing treatment-emergent potential injection site reactions that is judged to be related to study drug by the investigator will also be summarized and compared.

Table BDCL.2. List of MedDRA Preferred Terms (PTs) to Search for Injection Site Reaction Adverse Events (AEs)

Preferred Term	Preferred Term Code	Scope
Injection site abscess	10022044	Narrow
Injection site abscess sterile	10022045	Narrow
Injection site atrophy	10022048	Narrow
Injection site erythema	10022061	Narrow
Injection site hypertrophy	10022072	Narrow
Injection site induration	10022075	Narrow
Injection site infection	10022076	Narrow
Injection site inflammation	10022078	Narrow
Injection site irritation	10022079	Narrow
Injection site mass	10022081	Narrow
Injection site edema	10022085	Narrow
Injection site pruritus	10022093	Narrow
Injection site rash	10022094	Narrow
Injection site reaction	10022095	Narrow
Injection site warmth	10022112	Narrow
Injection site cellulitis	10050057	Narrow
Injection site swelling	10053425	Narrow
Injection site discomfort	10054266	Narrow
Injection site nodule	10057880	Narrow
Lipoatrophy	10024604	Narrow
Lipodystrophy acquired	10049287	Narrow
Partial lipodystrophy	10053857	Narrow
Lipohypertrophy	10062315	Narrow

Preferred Term	Preferred Term Code	Scope
Injection site bruising	10022052	Broad
Injection site haematoma	10022066	Broad
Injection site haemorrhage	10022067	Broad
Injection site pain	10022086	Broad

5.10.3.5. Systemic Hypersensitivity Reaction

The number and proportion of patients experiencing potential treatment-emergent systemic hypersensitivity reactions will be summarized and compared by treatment group using Fisher's exact test. The following MedDRA Standardized MedDRA Query (SMQ) will be used to identify potential systemic hypersensitivity reactions from all TEAEs:

- Anaphylactic reaction (SMQ). Besides using the narrow and broad terms designated within the SMQ, the following search algorithm will also be implemented as another approach to determine if a patient had an anaphylactic reaction: if a patient (had at least 1 event in Category A) or (had at least 1 event that is in Category B and also had at least 1 event that is in Category C) or (had at least 1 event that is in Category D and [also had at least 1 event in Category B or at least 1 event in Category C])
- Angioedema (SMQ)
- Hypersensitivity (SMQ)

Specifically, need to perform the following: (1) any narrow or algorithmic term from any 1 of the 3 SMQs indicated above (i.e., combined search across narrow and algorithmic portions of all 3 SMQs); (2) any narrow scope term within each SMQ, separately (i.e., narrow SMQ search); (3) any term within each SMQ, separately (i.e., broad SMQ search); (4) narrow scope term search within each SMQ, report the PT nested within each SMQ.

Note that an individual patient may contribute multiple events. Also, a single event may satisfy multiple SMQs, in which case the event contributes to every applicable SMQ.

5.10.4. Vital Signs and Body Weight

Vital signs and weight will be summarized by treatment group and visit. Change from baseline (last nonmissing value up to Visit 3) to postbaseline value for vital signs and weight will be summarized by treatment group and visit for patients who have both a baseline and at least 1 postbaseline result.

Treatment differences in mean change will be assessed using MMRM. The MMRM model will be used for the analysis during the treatment period and will contain the terms for treatment, baseline value, visit, and visit-by-treatment interaction as factors; patient as random effect; and CS as the variance-covariance structure. Only scheduled measures will be included in the MMRM analyses.

An analysis of covariance (ANCOVA) will also be conducted for the last nonmissing values during the study including the safety follow-up visit for the Safety Population. The ANCOVA model will use treatment, baseline value of the dependent variable as covariates.

The percentages of patients with treatment-emergent high or low vital signs at any time after randomization will be summarized and compared between treatment groups using Fisher's exact test. A treatment-emergent high result is defined as a change from a value less than or equal to the high limit (140 mm Hg for systolic blood pressure, 90 mm Hg for diastolic blood pressure, and 100 bpm for pulse) at baseline to a value greater than the high limit at any time that meets the specified change criteria after randomization. A treatment-emergent low result is defined as a change from a value greater than or equal to the low limit (90 mm Hg for systolic blood pressure, 50 mm Hg for diastolic blood pressure, and 50 bpm for pulse) at baseline to a value less than the low limit at any time that meets the specified change criteria after randomization. Patients with missing baseline measures will be excluded from this analysis unless otherwise specified. Scheduled visits, unscheduled visits, and retest measurements will be included in this analysis. Table BDCL.3 will be used to define the low and high limits and change thresholds.

Table BDCL.3. Categorical Criteria for Abnormal Treatment-Emergent Blood Pressure and Pulse Measurement

Parameter	Low	High
Systolic BP (mm Hg) (Supine or sitting)	≤ 90 and decrease from baseline ≥ 20	≥ 140 and increase from baseline ≥ 20
Diastolic BP (mm Hg) (Supine or sitting)	≤ 50 and decrease from baseline ≥ 10	≥ 90 and increase from baseline ≥ 10
Pulse (bpm) (Supine or sitting)	< 50 and decrease from baseline ≥ 15	> 100 and increase from baseline ≥ 15

Abbreviations: BP = blood pressure; bpm = beats per minute; mm Hg = millimeters of mercury.

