4.3. Exploratory Objectives

To investigate other safety and efficacy measures for LY3209590 for the following endpoints:

1. Insulin dose at baseline and Week 26;
2. Treatment-emergent adverse events (TEAEs);
3. Incidence and rate of hypoglycemia events during the post-treatment follow-up period;
4. Discontinuation of investigational product (IP) due to adverse events (AEs);
5. Clinical laboratory results;
6. Injection site reactions;
7. Liver aminotransferase change from baseline to Weeks 12 and 26;
8. Triglyceride and FFA change from baseline to Weeks 12 and 26;
9. Body weight change from baseline at Weeks 12 and 26;
10. Glucose time in target range, time in hyperglycemia, time in hypoglycemia using FGM
11. Lipids (cholesterol, LDL, HDL, triglycerides);
12. Six-point self-monitoring of blood glucose (SMBG) profiles;

13. The frequency of antibody formation to LY3209590;
14. Incidence and percentage of missed doses of LY3209590 and insulin degludec.

5. A Priori Statistical Methods

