A mixed-model repeated measures (MMRM) model will be used for continuous outcomes with repeated postbaseline measurements to compare treatment arms, unless otherwise noted. Treatment comparisons will be performed by the treatment difference in least-squares means (LS mean). Means and LS mean by treatment group and visit, along with the standard error of LS mean, 90% CIs of the treatment differences along with the p-value for the treatment comparison will be displayed. For the change from baseline, p-value for the within-treatment comparison will also be displayed. For selected parameters, log-transformed values will be analyzed in the MMRM model instead. The actual, change from baseline and percentage change from baseline will be presented using the derivation based on the output from the MMRM model.

In this study, the negative binomial regression will estimate Group Mean instead of LS mean and use delta method to estimate the standard error of the Group Mean (Qu and Luo 2015). Group Mean is defined as the mean response in the treatment group for the studied population. The difference between LS mean and the Group Mean is that LS mean estimates the response by

taking the inverse link function on mean covariates, while the Group Mean takes the inverse link function on individual patient covariates first and then averages over all patients.

Sensitivity analyses may be conducted for selected safety and efficacy measures by excluding data from patients who significantly deviated from the study dose algorithm, for example, patients who received repeated loading doses. The study team will review patient study dose data and identify the patients who will be excluded from the sensitivity analyses prior to the final lock of the study data.

All analyses will be implemented using SAS Enterprise Guide Version 7.1 or above.

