5.7. Primary Outcome and Methodology

The primary objective is to compare the HbA1c change from baseline to Week 26 between LY3209590 and insulin degludec and will be based on the primary estimand described below.

The primary estimand is the treatment differences in the change in HbA1c from baseline to 26 weeks for the targeted study population if all patients would adhere to the treatment without intercurrent events. The analysis data will include data up to the discontinuation of study treatment for the Efficacy Population with baseline and at least one non-missing postbaseline measurement. There may be missing values due to the early discontinuation of study treatment. The MMRM model will be used with the HbA1c changes at Week 6, 12, 16 and 26 (the primary endpoint) and the missing values will be imputed implicitly in the MMRM analysis under the assumption of missing at random. The MMRM model will include treatment (LY3209590 Algorithm 1, insulin degludec), strata (country, DPPIV [yes/no], SGLT2 [yes/no] and baseline BMI [<30 , ≥ 30]), visit, and treatment by visit interaction and the baseline value of the dependent

variable as the fixed effects. The HbA1c is reported in unit of % and will be converted to the unit of mmol/mol using the following formula: HbA1c in mmol/mol = 10.93*HbA1c in % - 23.5 (<http://www.ngsp.org/ifccngsp.asp>). HbA1c analysis will be conducted based on both units.

In the MMRM model, the within-patient errors are modeled as an unstructured variance-covariance matrix. If the analysis fails to converge, the following variance-covariance matrix will be used (in order) until one converges:

1. Toeplitz with heterogeneity
2. autoregressive with heterogeneity
3. compound symmetry with heterogeneous variances
4. Toeplitz
5. autoregressive
6. compound symmetry without heterogeneous variances

The Kenward-Roger approximation will be used to estimate denominator degrees of freedom for the MMRM models. The following is an example SAS code:

```
proc mixed data=DATA;  
  class TREATMENT STRATIFICATIONS VISIT PATIENT;  
  model HbA1c=BASELINE TREATMENT STRATIFICATIONS VISIT  
        VISIT*TREATMENT / solution ddfm=kr;  
  repeated VISIT / subject=PATIENT type=un;  
  lsmeans TREATMENT*VISIT/ pdiff cl alpha=0.1 om=DATA;  
run;
```

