5.10.5. Laboratory Measures

The data from laboratory testing will be summarized by treatment group and visit. Change from baseline (last nonmissing value up to Visit 3) to postbaseline value for laboratory tests (except for FSG, HbA1c, and Antibody) will be summarized for patients who have both a baseline and at least 1 postbaseline result. Treatment differences in mean change for these laboratory tests will be evaluated using MMRM model. The MMRM model will be used for the analysis during the treatment period and will contain the term for treatment, baseline value, visit, and visit-by-treatment interaction as factors, patient as random effect, and compound symmetric as the variance-covariance structure. Analyses will be provided in both international units (SI) and conventional units (CN). The MMRM analysis will only include lab tests for the scheduled visits specified in the protocol. For some selected laboratory measures, log-transformed value will be used in MMRM when necessary, and the geometric LS means as well as the percentage change from baseline will be reported.

The last nonmissing values during the study including the safety follow-up visit for the Safety Population will also be analyzed by an ANCOVA model. The ANCOVA model will use treatment, baseline value of the dependent variable as covariates. For some selected laboratory measures, log-transformed value will be used in the ANCOVA model.

The percentages of patients with treatment-emergent abnormal laboratory results at any time after randomization (including the treatment period and follow-up period) will be summarized

and compared between treatment groups using Fisher's exact test. A treatment-emergent abnormal result is defined as a change from normal at baseline to abnormal at any time after randomization. Covance reference ranges will generally be used to define the low and high limits. Patients with missing baseline lab measures will be excluded from this analysis unless otherwise specified. Scheduled visits, unscheduled visits, and retest measurements will be included in this analysis.

A lab listing in the Safety Population who had an treatment-emergent abnormal laboratory value during the study will be provided, including the actual measurement, abnormal result, and reference low or high limits.

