5.10.6. Electrocardiograms

Electrocardiograms will be collected at specific study visits. For Visit 3, 6, 9, 15 and 17, a triplicate ECG will be collected. The other visits, a single ECG will be collected. The average values will be used in the analysis.

The actual and change from baseline for selected ECG parameters (heart rate and intervals) will be analyzed using the MMRM model. The MMRM model will be used for the analysis during the treatment period and will contain the term for treatment, baseline value, visit, and visit-by-treatment interaction as factors, patient as random effect, and compound symmetric as the variance-covariance structure. The last nonmissing measurements will also be analyzed by the ANCOVA model with treatment and baseline value as covariates.

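### The safety MMRMs for weight, vital signs, laboratory tests and ECG pair a redundant random patient effect with compound symmetry, so by-visit intervals are wrong wherever variance differs by visit

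*SAP*

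**What the plan says.** SAP 5.10.4 models change in vital signs and weight over the treatment period with treatment, baseline, visit and visit-by-treatment, plus "patient as random effect; and CS as the variance-covariance structure". SAP 5.10.5 (laboratory) and 5.10.6 (ECG) do the same: "patient as random effect, and compound symmetric as the variance-covariance structure". None of the three sections names a fallback structure, a heterogeneous-variance version or a robust standard error.

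The primary HbA1c model in SAP 5.7 is specified differently. There, "the within-patient errors are modeled as an unstructured variance-covariance matrix", followed by six ordered fallbacks, of which "compound symmetry without heterogeneous variances" is the last.

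SAP 5.1 says what the MMRMs will report: "Means and LS mean by treatment group and visit, along with the standard error of LS mean, 90% CIs of the treatment differences". The endpoints in SAP 4.3 include "Body weight change from baseline at Weeks 12 and 26" and "Liver aminotransferase change from baseline to Weeks 12 and 26". On ECG replication, SAP 5.10.6 states: "For Visit 3, 6, 9, 15 and 17, a triplicate ECG will be collected. The other visits, a single ECG will be collected".

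**The concern.** There are two separate problems.

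- **Redundancy.** A random patient intercept adds a constant covariance between all visits of a patient. Compound symmetry does exactly the same. Specifying both leaves the split between them undetermined, and the programmer has to drop one.
- **Equal variance.** Homogeneous compound symmetry gives every visit the same variance, yet standard errors and intervals are reported visit by visit. If the spread of change increases over follow-up, the Week 26 standard error is averaged down by the quieter early visits, and the early ones are averaged up.

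The Week 26 safety intervals matter here. The protocol synopsis justifies the 26-week duration by the need to exclude an ALT increase, and names weight gain as a reason for including degludec. An interval that is too narrow can appear to exclude an increase that the data do not exclude.

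**Working it through.** **The plan's own figure.** The documents give no variance, standard error or power for any safety model. The only design figure is for HbA1c (Protocol 9.2: 100 completers per arm, SD 1.1%, margin 0.4%, two-sided alpha 0.1). It reproduces: SE = 1.1 × √(2/100) = 0.1556; 0.4/0.1556 − 1.645 = 0.926; power = Φ(0.926) = 82%, against the stated figure of more than 80%. It does not bear on this point.

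**Redundancy.** Let s² be the residual variance, c the compound-symmetry covariance and g the random-intercept variance. Then V = s²I + (c + g)J, where J is the matrix of ones. Three parameters enter but only two can be identified. (c, g) = (1, 0.5), (0.5, 1) and (1.5, 0) all give the same V, so estimates and standard errors do not depend on the split.

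**Equal variance.** With complete balanced data, compound symmetry estimates one variance equal to the mean of the visit variances. The Week 26 standard error, relative to the true one, is

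ratio = √(mean visit variance / Week 26 variance), and coverage of a nominal 90% interval = 2Φ(1.645 × ratio) − 1.

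Assumed inputs: postbaseline visits at Weeks 3, 6, 12, 16 and 26 (the schedule table is broken in the extracted text) and variance doubling linearly, v(t) = 1 + (t − 3)/23.

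- Visit variances: 1, 1.130, 1.391, 1.565, 2; mean 1.417.
- Ratio = √(1.417/2) = 0.842, so the Week 26 standard error is about 16% too small; coverage 83%.
- At Week 3, √(1.417/1) = 1.19, so that standard error is about 19% too large.
- The schedule appears to mark Week 24 for chemistry. Adding it (variance 1.913) gives a mean of 1.5 and a ratio of √(1.5/2) = 0.866, or about 13% too small; coverage 85%.

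**Other patterns, and dropout.** Here the SD changes linearly across five equally spaced visits. The last column is a simulation with 125 per arm, 20% monotone dropout, AR(1) correlation 0.8 and 600 runs per scenario.

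| SD, first to last visit | Complete data: ratio (coverage) | With dropout: ratio (coverage) |
|---|---|---|
| shrinks to 0.8 | 1.13 (94%) | not run |
| constant | 1.00 (90%) | 1.00 (90%) |
| ×1.25 | 0.90 (86%) | not run |
| ×1.5 | 0.84 (83%) | 0.83 (82%) |
| ×2 | 0.77 (80%) | 0.74 (76%) |
| ×3 | 0.71 (76%) | 0.67 (74%) |

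**ECG.** Suppose four postbaseline visits are triplicate averages, Visit 20 is a single reading, and replicate noise is a fraction f of single-reading variance. A triplicate average then has variance 1 − 2f/3, and ratio = √(1 − 8f/15). For f = 10%, 30% and 50% this is 0.97, 0.92 and 0.86, with coverage of about 89%, 87% and 84%.

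**The case against.** A reader might infer that the Week 26 error bars are simply wrong. The documents do not support that. They give no visit-specific variances; with constant variance the interval is right, and with shrinking variance it is conservative. Growth is plausible for weight, but no mechanism is evident for blood pressure, pulse or liver enzymes, and the liver enzymes are log-transformed first. More dramatic figures are possible only under stronger assumptions. Variance proportional to time gives a ratio of √(12.6/26) = 0.70 and 75% coverage, but that means an 8.7-fold rise (26/3).

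Nor does the redundancy damage inference. It may be one compound-symmetry model described in two ways, and at worst it produces a software warning or a parameter set to zero.

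The stakes are also limited. The objectives tables list weight and aminotransferase change as exploratory, although Protocol 8.2 places laboratory assessments among the secondary safety assessments. No decision rule uses these standard errors. Threshold tables for liver enzymes and Fisher tests for abnormal values do not depend on the covariance. For ECG, the extracted schedule shows no readable mark at Visit 20, so a single Week 26 reading is itself an assumption.

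All of this stands, and it limits the size of the point without removing it. The planned ANCOVA is no substitute, because it takes the last value including the follow-up visit and so does not give a Week 26 on-treatment interval. Kenward-Roger degrees of freedom, if meant to apply here, would not correct a misspecified covariance.

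**Conclusion.** The point holds in conditional form. As written, the three sections specify a model that is not identifiable. Once the redundant term is dropped, what remains is the structure that the SAP accepts only as a last resort for HbA1c, and no reason is given for using it here.

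By-visit standard errors and 90% intervals will be wrong wherever variance differs by visit. For weight, the likely direction at Week 26 is too narrow. For ECG, mixing triplicate averages with single readings makes unequal precision likely by design.

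The illustrative size of a 16% shortfall and 83% coverage (13% with a Week 24 visit) rests on the assumed visits, complete data and a linear doubling of variance, none of which the documents establish. The primary non-inferiority test uses its own unstructured model and is unaffected. This is a low-cost improvement to safety and mostly exploratory analyses.

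**What to change.** In SAP 5.10.4, 5.10.5 and 5.10.6, delete the random patient effect and refer to the covariance specification of 5.7: unstructured, the same ordered fallbacks, and Kenward-Roger degrees of freedom. If compound symmetry is kept for a measure, or the fallbacks end on an equal-variance structure, use heterogeneous variances or a sandwich standard error, and name the degrees-of-freedom method that goes with it.

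The cost is a wording change and an edited REPEATED statement. With five visits, an unstructured matrix has 5 × 6/2 = 15 parameters against 2 for compound symmetry, which is manageable with about 250 participants, and the fallback list covers non-convergence. If variance proves constant, little is lost.

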5.10.5. Laboratory Measures

The data from laboratory testing will be summarized by treatment group and visit. Change from baseline (last nonmissing value up to Visit 3) to postbaseline value for laboratory tests (except for FSG, HbA1c, and Antibody) will be summarized for patients who have both a baseline and at least 1 postbaseline result. Treatment differences in mean change for these laboratory tests will be evaluated using MMRM model. The MMRM model will be used for the analysis during the treatment period and will contain the term for treatment, baseline value, visit, and visit-by-treatment interaction as factors, patient as random effect, and compound symmetric as the variance-covariance structure. Analyses will be provided in both international units (SI) and conventional units (CN). The MMRM analysis will only include lab tests for the scheduled visits specified in the protocol. For some selected laboratory measures, log-transformed value will be used in MMRM when necessary, and the geometric LS means as well as the percentage change from baseline will be reported.

The last nonmissing values during the study including the safety follow-up visit for the Safety Population will also be analyzed by an ANCOVA model. The ANCOVA model will use treatment, baseline value of the dependent variable as covariates. For some selected laboratory measures, log-transformed value will be used in the ANCOVA model.

The percentages of patients with treatment-emergent abnormal laboratory results at any time after randomization (including the treatment period and follow-up period) will be summarized

and compared between treatment groups using Fisher's exact test. A treatment-emergent abnormal result is defined as a change from normal at baseline to abnormal at any time after randomization. Covance reference ranges will generally be used to define the low and high limits. Patients with missing baseline lab measures will be excluded from this analysis unless otherwise specified. Scheduled visits, unscheduled visits, and retest measurements will be included in this analysis.

A lab listing in the Safety Population who had an treatment-emergent abnormal laboratory value during the study will be provided, including the actual measurement, abnormal result, and reference low or high limits.

